8.4 Notification of deaths

Any SAE, SAR or unexpected SAR that results in death should be immediately reported to the sponsor, refer to section 8.3 for SAE reporting format and timelines.

Deaths occurring more than 30 days after the final dose, which are considered to be unrelated to the study medication, should not be reported as an SAE.

8.5 Pregnancy reporting

Pregnancy information for all female participants who become pregnant while participating in the study will be collected on the study specific Pregnancy Reporting Form and should be reported to the Sponsor via e-mail to [contact] or via the fax number provided on the SERF within 24 hours of becoming aware of the pregnancy or the pregnancy outcome. The participant will also be followed up to determine the outcome of the pregnancy, which will also be reported to the sponsor.

In the event of pregnancy, the participant may be withdrawn from the study (see Section 6.5).

Pregnancies in female partners of male participants should be reported as a special reporting situation (see Section 8.9).

8.6 Overdose

All participants should be counselled about the importance of taking the medications as prescribed and they should understand the quantity of medicine they should be taking. Participants must be told to contact their clinic immediately if they take too much medication. If the overdose fits the criteria of an SAE (see Section 8.1) it should be reported appropriately.

8.7 Reporting urgent safety measures

It is the responsibility of the investigator to apply the appropriate level of Urgent Safety Measure (USM) for the safety and protection of each participant in this study in order to prevent harm. USMs may be applied immediately without prior approval from the sponsor, CA or IRB/IEC. However, they must be reported to the sponsor and to the CI immediately (within 24 hours) who will then inform the CA and IRB/IEC according to local regulation.

8.8 Development Safety Update Reports

The sponsor will provide (in addition to the expedited reporting above) DSURs once a year throughout the clinical trial, or on request, to the CA and IRB/IEC. The sponsor intends to submit a single safety report on all investigational medicinal products used in the clinical trial in accordance with Article 43(2) of the Clinical Trial Regulation (EU) No 536/2014.

The report will be submitted within 60 days of the Developmental International Birth Date (DIBD) of the trial each year until the trial is declared ended.

8.9 Special Reporting Situations

Special reporting situations should be reported to the sponsor via email to [contact] within 24 hours of the research staff becoming aware of the event (as for SAEs).

The special situations include:

- Pregnancy exposure (maternal and paternal), breastfeeding and AEs in infants following exposure from breastfeeding
- Overdose (other than as defined in section 8.7), suspected abuse/misuse of the study product, and dependence
- Medication error
- DDI
- Inadvertent or accidental exposure to the study product (including occupational exposure)
- Any failure of expected of pharmacological or medical device action (i.e. lack of effect) of study product
- Unexpected therapeutic or clinical benefit from use of the study product
- Suspected transmission of an infectious agent via the study product
- Expired drug use and falsified medicine
- Off-label use of study product

Product Quality Complaint (PQC): Any written, electronic, or oral communication that alleges deficiencies related to the identity, quality, durability, reliability, safety, effectiveness, or performance of a study product after it is released for distribution. A complaint is any indication of the failure of the product to meet consumer or user expectations for quality or to meet performance specifications. It may allege an AR, injury, or malfunction associated with the use of the product. It may also involve the design, literature, packaging, advertising, availability, physical appearance, or promotion of a product.

9 STATISTICS AND DATA ANALYSIS

9.1 Sample size calculation

In the ANRS 146 OPTIMAL trial [Levy et al.], of late presenters, the proportion of patients with severe morbidity (new adverse drug event (ADE), other HIV related diseases, serious non-AIDS events, IRIS and death) was estimated at 12.2% per year in the boosted PI arm. The virological failure was estimated at 20% at week 48 in the DRV/r group of the IMEA 040 DATA study (Slama L et al) that recruited a similar population. As a few subjects will meet more than one of these criteria, we assumed a cumulative probability of failure at 25% at 48 weeks in the PI regimen group.

A total of 404 evaluable subjects, randomized in a 1:1 ratio to 2 treatment groups (202 subjects per treatment group), achieves at least 80% power to detect a non-inferiority margin of 1.606 in the hazard ratio, which corresponds to a 12% difference in the cumulative probability of failure rate between INI-based regimen group (37%) and PI-based regimen group (25%), with 97 events required. The sample size and power calculation assumes that the cumulative probability of failure is 25% for the PI regimen group and 23% for the INI-based regimen group (i.e. the expected hazard ratio is 0.909), using a non-inferiority margin of 1.606 in hazard ratio and a two-sided 95% confidence interval (CI). The sample size and power calculation were made using the statistical software package nQuery Advanced, non-inferiority testing of two survival curves using cox regression module (Version 8.1.2.0). With an estimated ~7.5% drop off rate/year, we plan to enroll 220 subjects per group to ensure we have sufficient power for this per-protocol analysis.

Superiority of INI-based regimen group versus PI-based regimen group will be evaluated after the non-inferiority is established. With an ITT analysis, 440 subjects and 78 events, a two-sided log-rank test at an alpha level of 0.05 will achieve at least 80% power to detect a 50% reduction in hazard rate in INI-based regimen (i.e. the hazard ratio is 0.5). A 50% reduction in hazard rate means that INI-based regimen could decrease the risk by 11.6% (25% for PI- vs 13.4% for INI- based regimen).

9.2 Planned recruitment rate

In the ANRS 146 OPTIMAL trial, in which similar patients were enrolled (late presenters with low CD4 cell count or ADE), 10% of screened patients were not eligible. Based on this information, we estimated that about 489 patients should be screened. Centres of NEAT ID Network with infectious disease units for inpatient and outpatient care will be the prioritised study sites of the LAPTOP Trial. We expect that about 45 sites in total across eight European countries. Therefore, we estimated that about 7-15 patients should be screened per site.

9.3 Statistical analysis plan

These analyses will assess the efficacy and safety of BIC containing regimen in comparison with the boosted PI containing regimen.

All randomised patients who received at least 1 time any study treatment will be included in the intent-to-treat (ITT) analysis population. Of note patients lost-to follow-up or violating the protocol will not be excluded from the ITT population. Patients who switch treatment to another will be analysed as if they are remained in their initial randomisation group. All participants who are lost to follow-up or discontinued the study when they are endpoint free at time of leaving the study will be censored at the time of leaving the study. We will use time-to-event methods, including Kaplan–Meier survival curves and Cox proportional-hazards models to account for all participants in the analysis. The per-protocol population will include all patients from the ITT population except those who did not fulfil the inclusion/exclusion criteria, who withdrew their consent, gave up, lost to follow-up or discontinued early study medication for any reasons other than any component of the primary endpoint.

9.3.1 Summary of baseline data and flow of patients

All continuous variables will be summarised using the following descriptive statistics: n (non-missing sample size), mean, standard deviation (SD), 1st quartile, median, 3rd quartile, maximum and minimum. The frequency and percentages (based on the non-missing sample size) of observed levels will be reported for all categorical variables.

The number of patients and the flowchart of the study will be presented. The period of enrolment and the total number of patients screened to be included in the study will be presented. The number of ineligible patients and the total number of randomised patients will be presented. The number of patients who never take the study treatment will also be presented by group and those who remained on the study treatment up to week 48 will be presented.

9.3.2 Primary outcome analysis

The primary outcome analysis will be performed with both ITT population and per-protocol population. The primary endpoint is the occurrence of a severe morbidity (virological failure; death related to HIV, AIDS, OI/severe BI or complications of therapy including IRIS; new ADE; new serious non-AIDS events; and clinically relevant AEs of any grade leading to study treatment discontinuation). The effect of study treatment will be assessed using Cox regression model with treatment group and adjustments for stratification factor (participating country and baseline CD4 cell counts). Separate

analyses for each component of the primary endpoint will be done. Kaplan-Meier curves will be plotted for the primary endpoint and its component.

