5.2.2 Per Protocol Population

The per-protocol (PP) population will include all participants from the mITT population, with the exception of those who did not meet the inclusion/exclusion criteria or who initially received treatment assigned to the other group.

The PP and DPS2 will be used for sensitivity analyses of the primary endpoint.

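### Protocol and SAP give the per-protocol set different roles and definitions, the protocol's definition selects on outcome, and neither says which population is tested against 1.606

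*Combined protocol and SAP*

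**What the plan says.** **Role of PP.** Protocol v5.0 section 9.3.2: "The primary outcome analysis will be performed with both ITT population and per-protocol population". No order is set between the two, and nothing says that both must succeed. Section 9.1 adds that "we plan to enroll 220 subjects per group to ensure we have sufficient power for this per-protocol analysis". SAP v0.3 section 5.2.1 assigns the primary endpoint to mITT with DPS1 (all observed data). On PP, section 5.2.2 says: "The PP and DPS2 will be used for sensitivity analyses of the primary endpoint". SAP sections 7 and 7.1 repeat this, yet SAP section 4 keeps the protocol's statement that enrolment is set for the PP analysis.

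**Definition of PP.** Protocol section 9.3, repeated in substance in 9.6, removes ineligible patients, those who withdrew consent, gave up or were lost, and those who "discontinued early study medication for any reasons other than any component of the primary endpoint". SAP section 5.2.2 takes the mITT set "with the exception of those who did not meet the inclusion/exclusion criteria or who initially received treatment assigned to the other group". With DPS2 it keeps discontinuers and discards only their data after discontinuation or rescue.

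**Status of the texts.** The SAP (November 2023) says that it rests on protocol v2.0. Protocol v5.0 is dated March 2024. Neither says which prevails. Protocol section 9.8 sends major analysis changes through an amendment.

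**The concern.** A non-inferiority claim needs its deciding analysis fixed in advance. Here PP is a joint primary analysis and the basis of the sample size in one document, and a sensitivity analysis in the other. The two PP sets contain different patients. If the mITT and PP limits fell on opposite sides of 1.606, no text would say how to conclude, and the choice could be made with the results in view.

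The protocol's PP rule has a fault of its own. A patient who stops drug because of an endpoint stays in and counts as an event. A patient who stops event-free for another reason disappears with all event-free time. Membership therefore depends on what happened after randomisation. If such departures are more common in one arm, that arm's failure risk is inflated relative to the other.

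**Working it through.** **1. The plan's own figures** (protocol 9.1, SAP 4: risks 25% PI and 23% INI, margin 37% vs 25%, two-sided 95% CI, 80% power, about 7.5% loss).

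- Margin: ln(0.63)/ln(0.75) = 0.4620/0.2877 = 1.606.
- Expected HR: ln(0.77)/ln(0.75) = 0.2614/0.2877 = 0.909.
- Events: (1.960 + 0.842)² / [0.25 × (ln 1.606 − ln 0.909)²] = 7.849 / (0.25 × 0.5692²) = 96.9, so 97.
- Evaluable: 96.9/0.24 = 403.8, so 404. Enrolled: 404/0.925 = 436.8, so 437, against 440 planned.

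The figures reproduce. The sample-size arithmetic is not at fault.

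**2. The texts side by side**

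| | Protocol v5.0 | SAP v0.3 |
|---|---|---|
| Primary analysis | ITT and PP (9.3.2) | mITT with DPS1 (5.2.1, 7.1) |
| Role of PP | joint primary | sensitivity (5.2.2, 7, 7.1) |
| Sample size is for | PP (9.1) | PP (4) |
| Event-free discontinuer in PP | deleted (9.3, 9.6) | kept, follow-up cut (DPS2) |
| Population whose limit is tested against 1.606 | not stated | not stated |

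**3. Effect of the protocol's PP rule.** The documents give no discontinuation rate by arm, so the rates here are assumptions. Take exponential times over 48 weeks, with discontinuation independent of failure. For 48-week failure risk p and non-endpoint discontinuation d, set λ = −ln(1−p) and μ = −ln(1−d). The protocol keeps patients with an event first (E) or with neither (S):

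- E = λ/(λ+μ) × (1 − e^−(λ+μ)); S = e^−(λ+μ)
- PP risk = E/(E+S); HR = ln(1 − risk INI)/ln(1 − risk PI)

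True HR 1.606, with d = 5% INI and 15% PI:

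- INI: λ 0.4620, μ 0.0513, E 0.3614, S 0.5985, risk 0.3765.
- PI: λ 0.2877, μ 0.1625, E 0.2316, S 0.6375, risk 0.2665.
- HR = 0.4724/0.3099 = 1.52.
- Events: 220 × (0.3614 + 0.2316) = 130.5; SE = 2/√130.5 = 0.175.
- False non-inferiority: Φ[(ln 1.606 − ln 1.524)/0.175 − 1.960] = Φ(−1.66), about 5%. Without bias it is Φ(−1.960) = 2.5%.

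True HR 0.909:

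- Same rates: risks 0.2348 and 0.2665, HR = 0.2676/0.3099 = 0.86.
- Reversed (15% INI, 5% PI): risks 0.2456 and 0.2551, HR = 0.2818/0.2945 = 0.957, so about 0.95 to 0.96.

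Equal 7.5%: a true 1.606 gives 1.603 and a true 0.909 gives 0.909.

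A Cox simulation (440 patients, 1,500 runs per scenario) agrees. At 20% PI and 5% INI, false non-inferiority is 7.5% under the protocol rule and 2.2% under the SAP rule. At 10% and 5% it is 3.9% and 3.1%, with simulation error of about 0.5 points. At an equal 7.5% both rules give 0.904 for a true 0.909.

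**4. Power by deciding population** = Φ(0.5692/2 × √D − 1.960).

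- mITT alone, full follow-up: D = 440 × 0.24 = 105.6, power 83.3%.
- PP of 404 alone: D = 97, power 80.0%.
- Both required: correlation √(404/440) = 0.96 for nested sets; the bivariate normal gives 78.3%. At correlation 0.90 or 0.80 it is 76.7% or 74.8%.

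**The case against.** **A split result.** A reader might infer that, on a split, the protocol calls the primary analysis divided while the SAP declares non-inferiority. The documents do not support this. The protocol says only that both analyses are run, and SAP section 7.1 compares no limit with 1.606. SAP Table 2 also prints the mITT and PP hazard ratios together, so a split would be visible.

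**ITT versus mITT.** This is not a conflict. Both sets are randomised patients with at least one dose.

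**Size.** It is tempting to quote about 8% false non-inferiority and an HR of 1.46 at 5% vs 15%, from the shortcut p/(1 − d(1−p)). That formula deletes only patients who would have stayed event-free to week 48. Discontinuers who would have failed later are deleted too, which dilutes the bias. Even the 5% applies only if the protocol's PP set alone decides. If ITT must also pass, the error cannot exceed that of ITT, 2.5%.

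**Imbalance.** The only rate given is about 7.5% per year overall, and adverse-event or IRIS interruptions longer than 5 days are already endpoints. That stands, so the size is conditional. Some imbalance is plausible: the trial is open-label, protocol 1.2.2 expects fewer drug interactions with INI, and the resistance rule in 6.1.3 that moves patients between the trial arms runs only from DRV to BIC. Direction is open, since 6.5 makes stopping in pregnancy mandatory only for B/F/TAF.

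**Wording.** Section 9.3 does not say that withdrawn or lost patients must be event-free to be removed. The calculation assumes that they are.

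**Independence.** Censoring at discontinuation is not free of bias either. In simulations where discontinuation and failure shared a risk factor (20% PI, 5% INI), the ITT HR was 0.923, the protocol PP 0.922 and the SAP PP 0.981. With the rates reversed they were 0.912, 0.909 and 0.853. This limits what either PP set can carry alone. It does not remove the inconsistency.

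**Dates.** A reader might take the later date of v5.0 as a decision to keep the PP rule. The amendment tables from v2.0 to v5.0 list only 9.5 within section 9, so this is carried-over text.

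**Conclusion.** The point holds as an inconsistency and an omission. The role of PP differs between the documents, and the SAP is inconsistent with itself on what the sample size serves. The PP definitions differ in substance. No rule ties a named population to 1.606.

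The protocol's PP definition also selects on a post-randomisation outcome. Under independent discontinuation, its effect is negligible when rates are equal and modest at an assumed 5% vs 15%: 1.606 moves to about 1.52, and 0.909 to about 0.86, or to 0.95–0.96 with the rates reversed. The bias can go either way. The documents do not show that an imbalance will occur, or that the trial would reach a wrong conclusion. This should be corrected, and it can be: SAP section 5.1 provides for an update before sign-off.

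**What to change.** 1. Replace the PP definition in protocol 9.3 and 9.6 with the SAP's: exclude eligibility violators and wrong initial regimen and, with DPS2, cut follow-up at discontinuation or rescue instead of dropping the patient. State the non-informative censoring that this assumes.
2. Give PP the same role in protocol 9.1 and 9.3.2 and in SAP sections 4, 5.2 and 7.1.
3. Before database lock, state which population's upper 95% limit is tested against 1.606, with superiority on mITT.

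The sponsor has a real choice in step 3. mITT with PP as sensitivity is coherent; so is requiring both. Requiring both lowers power to about 78% with a PP set of 404, so the stated 80% would need restating.

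The cost is wording in the SAP and a protocol amendment under section 9.8. No data collection changes.

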9.3.3 Secondary outcome analysis

All secondary outcome analysis will be done with the ITT population. The p-values will be two-tailed, with a significant level of 0.05.

The proportion of patients with HIV-ribonucleic acid (RNA) viral load <50 copies/mL at week 48 will be analysed using the snapshot approach. Fisher's exact test will be used to compare the estimated proportion between the two groups.

A genotypic resistance test will be performed in all patients with virological failure. Drugs resistance mutations will be identified from the International AIDS Society (IAS)-USA resistance testing panel (last version at the time of analysis) and for BIC we will use IAS, Agence Nationale de Recherches sur le SIDA (National Agency for AIDS Research) (ANRS) or Royal College of Physicians (RCP) lists to perform the analysis whenever they will be made available. Resistance to BIC will also be identified using phenotypic resistance test. Fisher's exact test will be used to compare the presence of at least one drug resistance mutation between the 2 groups.

The median time to reach CD4 cell count >200/ μ l will be estimated using the Kaplan-Meier method, censoring at week 48 or last follow-up date if not seen at week 48. Time to reach CD4 cell count >200/ μ l will be defined as the time between the date of study treatment initiation (baseline, week 0) and the date of which patient reached CD4>200/ μ l. The log-rank test will be used to compare the two survival functions. The p-values will be two-tailed, with a significant level of 0.05. The proportion of patients with CD4 cell count <350/ μ l at week 48 will be done with the ITT population, with the last observation carried forward (LOCF) approach. Fisher's exact test will be used to compare the 2 groups.

The median change in CD4/CD8 ratio from baseline to week 48 will be analysed with the ITT population, with the LOCF approach. The non-parametric Mann Whitney test will be used to compare the change from baseline between the 2 groups.

The incidence of IRIS will be analysed with the Kaplan-Meier method. The Log-rank test will be used to compare the two survival functions. The effect of study treatment on IRIS will be assessed using Cox regression model with treatment group and adjustments for stratification factors.

The incidence of hospitalisation will be estimated by the Kaplan-Meier estimate. The Log-rank test will be used to compare the two survival functions. The duration of hospitalisation will be estimated by the cumulative days of hospitalisation during the course of study and will be compared between the 2 groups by using the Mann-Whitney test. The rate of relapse/recurrence will be estimated by the number of patients with relapse/recurrence divided by the total number patients in ITT population. Fisher's exact test will be used to compare the 2 groups.

The frequency of each Grade 2, 3 or 4 AEs, laboratory toxicities, and ART and OI/BI treatment changes and dose modifications due to toxicities and IRIS will be described and compared by group. Fisher's exact test will be used to compare the 2 groups.

The proportion of patients with health care resource use, and emergency room visits will be compared in the two groups with Fisher's exact test. The total inpatient days will be estimated by the cumulative inpatient days during the course of study and will be compared between the 2 groups by using the Mann-Whitney test.

To assess the impact of study treatment on the evolution of QOL at week 48, we will use multiple imputation approach to replace missing values. We will compare the treatment effect on QOL on each of the 5 datasets generated, including the imputed values, and the results will be combined with Rubin's rules. A generalized estimating equation (GEE) model will be used.

9.4 Subgroup analyses

Subgroup analyses for the primary endpoint will be done to explore whether estimated treatment effects vary significantly between subcategories of trial participants. The following variables will be assessed: age, gender, transmission group, ethnic group, baseline CD4 (<50, 50-199, ≥200), baseline viral load (<100,000, 100,000-500,000, >500,000), smoker, adherence (>/< 95%) and participating country. Heterogeneity of the treatment effect across subgroups will be assessed by including terms for interactions between treatment and subgroup variables in expanded Cox models. Age will be divided into three groups using tertiles/quartiles.

9.5 Interim analysis and criteria for the premature termination of the trial

No formal interim analysis will be done. However, a DSMB will be established and will review the data regularly during the course of the study (see Section 12 of the protocol for more details).

There is no trial-specific stopping criterion as the trial involves licensed products used within the marketing authorisation dosing instruction.

9.6 Subject population

All randomised patients who received at least 1 time any study treatment will be included in the ITT analysis population. Of note patients lost-to follow-up or violating the protocol will not be excluded from the ITT population.

The per-protocol population will include all patients from the ITT population except those who did not fulfil the inclusion/exclusion criteria, who withdrew their consent, gave up, lost to follow-up or discontinued study medication for any reasons other than study endpoint criteria.

